7.2 IMPLANT/PROCEDURE/PRE-DISCHARGE

After it is verified that the subject meets preliminary study enrollment criteria, the implant procedure can be scheduled.

The procedure TEE can serve as the baseline TEE to rule out the presence of intracardiac thrombus (including left atrial appendage thrombus) and to assess size and shape of the LAA.

See the IFU for procedural and post-procedural instructions (refer also to **Table 2**).

7.3 SCHEDULED FOLLOW-UPS

Scheduled office visits occur at 45 days (+45 days), 6M (+/- 3 weeks) 12M (+/- 6 weeks) and 24 M (+/- 6 weeks) post procedure;

Phone contact follow up visits occur at, 36M (+/- 6 weeks), 48M (+/- 6 weeks) and 60 M (+/- 6 weeks) post procedures.

Refer to Table 2 for required follow-up testing and assessments.

7.4 INTERIM/UNSCHEDULED VISITS

Interim/unscheduled visits will be considered those that occur in addition to the required visit interval schedule. If an unscheduled or interim visit occurs, an adverse event assessments eCRF or deviation form, as applicable should be completed to capture data collected at the visit. In the event of a confirmed stroke or TIA, TEE should be conducted within 14 days from the date the site becomes aware of the event and the modified Rankin Scale eCRF should be completed 90 days after the event.

7.5 DESCRIPTION OF ACTIVITIES PERFORMED BY SPONSOR REPRESENTATIVES

Trained Sponsor personnel may perform certain study activities to ensure compliance to the clinical protocol. Monitoring may be performed by SJM and/or authorized designees according to the CFDA regulations, the monitoring plan and applicable SJM standard operating procedures and work instructions. Qualified monitors will ensure investigators comply with this clinical protocol and CFDA regulations.

To ensure study personnel accept, understand and complete their assigned responsibilities, monitors, field clinical personnel, and/or clinical country managers, may perform periodic site visits during the course of the study. These actions will help to ensure the continued acceptability of the facilities, compliance to the clinical protocol and relevant regulations, and the maintenance of complete records. Monitoring will include review and resolution of missing or inconsistent results and source document verification (i.e. comparison of submitted study results to original reports) to assure the accuracy of the reported data.

Sponsor representatives will periodically request source documents, resolution of discrepancies, submission of echocardiography imaging etc. for data cleaning and reporting purposes.

7.6 SUBJECT STUDY COMPLETION

Subjects will complete their participation in the study at the 5-year follow-up visits and will return to receiving medical care per their physician's recommendations.

Clinical Investigational Plan

7.7 CRITERIA AND PROCEDURES FOR SUBJECT WITHDRAWAL OR DISCONTINUATION

Subjects must be informed about their right to withdraw from the study at any time and for any reason without sanction, penalty or loss of benefits to which the subject is otherwise entitled and withdrawal from the study will not jeopardize their future medical care or relationship with the investigator. Subjects will be asked to specify the reason for the termination, but have the right not to answer.

The investigator may decide to withdraw a subject from the study at any time with reasonable rationale. The subject's future care will not be influenced by a decision, voluntary or otherwise, to withdraw from the study. All reasonable efforts should be made to retain the subject in the clinical study until completion of the study.

Reasons for subject's withdrawal include, but are not limited to:

- Subject refuses to continue participating in the study
- Withdraw subjects who have an unsuccessful implant 7 days after the date of the attempted procedure.
- Subject is deceased (cause must be documented)
- Subject's non-compliance
- Subject is 'lost to follow up': Subject does not adhere to the scheduled follow up visits but has not explicitly requested to be withdrawn from the clinical study. (This does not apply to missed visits).

Site personnel should at all times make all reasonable efforts to locate and communicate with the subject in order to achieve subject compliance to the scheduled follow up visits:

1. A subject will be considered 'Lost to Follow Up' after a minimum of 2 phone calls of a physician or delegate at the investigational site to the subject or contact. These 2 phone calls need to be documented in the subject's study charts and/or medical record.
2. If these attempts are unsuccessful, a letter should be sent to the subject's last known address or general practitioner (GP) and a copy of this letter should be maintained in the subject's study charts and/or medical record.

Note: If a subject misses one or more of the scheduled follow up visits (inclusive of the assigned visit windows), this will be considered as a missed visit. The subject may therefore still return for subsequent visits and will not be excluded from the study.

If a subject withdraws from the clinical study, the site will record the subject's reasons for withdrawal, on a Withdrawal CRF.

When subject withdrawal from the clinical study is due to an adverse event the subject will be followed until resolution of that adverse event or determination that the subject's condition is stable. The status of the subject's condition should be documented at the time of withdrawal.

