9.2 PROCEDURE FOR ASSESSING, RECORDING, AND REPORTING ADVERSE EVENTS

Safety surveillance within this study and the safety reporting performed both by the investigator and Sponsor starts as soon as the procedure begins, which is defined as the time the dilator/device delivery system has been introduced into the body. The safety surveillance and the safety reporting will continue until the last visit has been performed, the subject is deceased, the subject/investigator concludes his participation into the study or the subject/investigator withdraws the subject from the study.

For the purposes of this study, the following AEs will be collected:

- All AEs (regardless of seriousness)
- All SAEs (regardless of relatedness)
- In addition, the following event types will also be reported
- device embolization, device erosion, clinically significant device interference with surrounding structure, device thrombus, device fracture, device infection (endocarditis / pericarditis), device perforation, device laceration, or device allergy

All AE data will be collected throughout the clinical study and will be reported to the Sponsor through the EDC system. The Investigator will record all AE on the appropriate eCRF as soon as possible, but no later than 5 working days of first learning of the event.

For any SAE (including deaths) and any SADE, the investigator shall notify the Sponsor through the EDC system immediately (but no later than 3 working days) of the investigator's awareness of the event and provide the Sponsor with all necessary documentation needed. The Sponsor will notify relevant regulatory authorities and all the other participating sites no later than 5 working days after awareness of the event.

Clinical Investigational Plan

The investigator and Institution will report SAE (including deaths) and SADE to the IRB/EC / relevant regulatory authorities no later than 24 hours of first learning of the event per CFDA's regulations.

Records relating to the subject's subsequent medical course must be maintained and submitted (as applicable) to the Sponsor until the event has subsided or, in case of permanent impairment, until the event stabilizes and the overall clinical outcome has been ascertained. Additional information may be requested, when required, by the Sponsor in order to support the reporting of AEs to regulatory authorities.

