13.1.2 Primary safety endpoint (Long-Term)

The long-term safety endpoint is the 2-year occurrence of device embolization, device erosion, clinically significant device interference with surrounding structure, device thrombus, device fracture, device infection (endocarditis / pericarditis), device perforation, device laceration, or device allergy.

[REDACTED]

[REDACTED]

Clinical Investigational Plan

Hypothesis:

$$H_0: p_l \geq PG_l$$

$$H_1: p_l < PG_l$$

where p_l is the long-term safety endpoint event rate. It is assumed that the long-term safety endpoint event rate is 5%. [REDACTED]

[REDACTED]

[REDACTED]

[REDACTED] An event rate of 5% is assumed for the long-term safety endpoint for the ACP device [REDACTED]

[REDACTED] The performance goal, PG_l , is set at 10% [REDACTED]

[REDACTED]

[REDACTED]

[REDACTED]

Analysis Methods:

Kaplan-Meier survival analysis will be used to estimate the event rate of at 24 months (731 days post implant). [REDACTED]

[REDACTED]

Sample Size Determination:

The sample size is estimated assuming an event rate of 5%. A sample size of 231 subjects followed through 24 months will provide 80% power at the 2.5% significance level. Assuming an attrition rate of 25% through 24 months, 308 subjects are required to be enrolled in the study.

Analysis Population:

Enrolled subjects will be included in this analysis.

13.1.3 Primary effectiveness endpoint:

The primary effectiveness endpoint is the composite endpoint of ischemic stroke or systemic embolism at 2 years.

Hypothesis:

$$H_0: p_e \geq PG_e$$

$$H_1: p_e < PG_e$$

where p_e is the event rate at 24 months. [REDACTED]

[REDACTED]

[REDACTED]

[REDACTED] The performance goal, PG_e is set at 9%, [REDACTED]

[REDACTED]

[REDACTED]

Analysis Methods:

[REDACTED]

Clinical Investigational Plan

Kaplan-Meier survival analysis will be used to estimate the event rate of at 24 months (731 days post implant). XXXXXXXXXX

Sample Size Determination:

A sample size of 257 subjects followed through 24 months will provide 80% power at the 2.5% significance level assuming a 24-month event rate of 4.5%. Assuming an attrition rate of 25% through 24 months, 343 subjects are required to be enrolled in the study.

Analysis Population:

Enrolled subjects who receive an implant of the ACP device will be included in the analysis.

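### Sections 7.7 and 9.2 together let a subject be withdrawn for non-compliance and then stop endpoint collection, so censoring of both 24-month primary endpoints may be informative

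*Combined protocol and SAP*

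**What the plan says.** **Withdrawal (section 7.7).** The investigator has open discretion: "The investigator may decide to withdraw a subject from the study at any time with reasonable rationale". The listed reasons include "Subject's non-compliance", which is not defined. The same section asks sites to make every reasonable effort to keep subjects in the study. It says of a subject who misses visits: "The subject may therefore still return for subsequent visits and will not be excluded from the study". The reason for withdrawal goes on a Withdrawal CRF. The closing paragraph adds that a subject withdrawn because of an adverse event is followed until that event resolves or the condition is stable, and that the subject's condition is documented at withdrawal.

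**End of event collection (section 9.2).** Surveillance and reporting run until the last visit, death, or the point at which "the subject/investigator concludes his participation into the study or the subject/investigator withdraws the subject from the study".

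**Schedule (Table 2, section 7.3).** After month 6, scheduled contacts up to the primary time point are at 12 and 24 months. Table 2 has no column for an assessment at withdrawal.

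**Analysis and size (sections 13.1.2 and 13.1.3).** Both 24-month primary endpoints are estimated by Kaplan-Meier at 731 days. For effectiveness: "A sample size of 257 subjects followed through 24 months will provide 80% power at the 2.5% significance level", with an assumed rate of 4.5% against a goal of 9%. Then: "Assuming an attrition rate of 25% through 24 months, 343 subjects are required to be enrolled in the study". Text after the Kaplan-Meier sentences is blacked out.

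**The concern.** The subject already carries the implant. Ending study participation for non-compliance removes no study treatment and, on the visible text, serves no stated purpose. Its effect is to stop the recording of strokes, emboli and device events. Section 7.7 also pulls two ways: a missed visit does not exclude a subject, yet undefined non-compliance can. Two sites could therefore treat the same subject differently.

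Kaplan-Meier is unbiased only if those censored have the same later risk as those who stay. Subjects who do not keep to visits or antithrombotic treatment could plausibly have more device thrombus and stroke. If so, both 24-month rates come out too low. Section 13.4 requires all three primary endpoints to be met, and two of them are exposed. Inflating enrolment for 25% attrition protects power. It does not protect against this bias.

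**Working it through.** **1. The plan's own figures.** Inputs from sections 13.1.2 and 13.1.3: one-sided alpha 2.5%, power 80%, 25% attrition. Using an exact binomial test, take the largest c with P(X ≤ c | n, goal) ≤ 0.025.

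- Effectiveness, 9% against 4.5%: n = 257, c = 14, alpha 0.0241, power 81.5%; 257/0.75 = 342.7, so 343.
- Long-term safety, 10% against 5%: n = 231, c = 14, alpha 0.0239, power 81.6%; 231/0.75 = 308.

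All stated sizes reproduce. None of them is in question here.

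**2. What follows from the text.** 7.7 permits withdrawal for non-compliance. 9.2 ends reporting at that moment. The only stated continuation is for an adverse event that caused the withdrawal. A stroke two months after a non-compliance withdrawal therefore has no stated route into the data.

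**3. How large the bias could be.** The documents give neither the number of such withdrawals nor the risk of those subjects. These are assumptions:

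- a share q leaves, with exits spread evenly over 24 months;
- the 24-month risk is p = 4.5% in those retained and k·p in leavers;
- hazards are constant, and event status is complete up to exit.

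True rate = (1 − q)·p + q·k·p.

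For the rate that Kaplan-Meier estimates, let u = time/24 months, h0 = −ln(1 − p) and h1 = −ln(1 − k·p). The weights at risk are a(u) = (1 − q)·exp(−h0·u) and b(u) = q·(1 − u)·exp(−h1·u).

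Kaplan-Meier rate = 1 − exp{−∫ from 0 to 1 of [a·h0 + b·h1]/(a + b) du}.

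| q | k | True rate | Kaplan-Meier | Understatement |
|---|---|---|---|---|
| 10% | 2 | 4.95% | 4.74% | 0.2 points |
| 25% | 2 | 5.63% | 5.12% | 0.5 points |
| 25% | 3 | 6.75% | 5.75% | 1.0 point |

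Hand check for q = 25%, k = 2, ignoring depletion by events. The leavers' average weight is 1 + ((1 − q)/q)·ln(1 − q) = 1 + 3·ln 0.75 = 0.137. The hazards are h0 = 0.0460 and h1 = 0.0943. The cumulative hazard is 0.0460 + 0.137 × 0.0483 = 0.0526, a rate of 5.1%.

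**4. An upper bound.** Suppose instead that leavers exit right after implant and the true effectiveness rate equals the 9% goal. The chance of wrongly meeting the goal is then 4.7% (q = 10%, k = 2), 16.7% (25%, 2) or 41.9% (25%, 3), against at most 2.4% when k = 1. In these cases leavers contribute no follow-up. The 25% cases also treat all planned attrition as high-risk.

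**The case against.** The section has real safeguards. Sites must try to retain subjects, missed visits do not exclude, and loss to follow-up needs at least two documented calls, with a letter if they fail. The list of reasons is permissive: only the failed-implant line directs a withdrawal. Adverse events are reportable as they become known and at unscheduled visits, so detection up to withdrawal does not depend on the 12- and 24-month contacts alone. All of this stands and makes the likely number of non-compliance withdrawals smaller. None of it collects an event after withdrawal.

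Several stronger readings are tempting, and the documents do not support them:

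- *Only the reason is recorded at exit.* The end of 7.7 also asks for the subject's condition. It does not ask whether an endpoint event has occurred since the last assessment, and the Withdrawal eCRF's fields are not shown.
- *A subject withdrawn at month 22 and last seen at month 12 is counted event-free to month 22.* No visible text gives the censoring date, and the relevant text is blacked out.
- *The bias would flip the result.* Setting a true rate of 5% to 6.8% against the limit of 14 events in 257 (5.4%) compares a true rate with a limit for observed events. The benchmark for the truth is the 9% goal, and every row of the table stays below it, so declaring success would be correct in each.
- *The whole 25% attrition is selective.* That allowance can also cover deaths, refusals and ordinary loss to follow-up, which deleting one reason would not prevent.

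**Conclusion.** The concern holds as a gap in 7.7 and 9.2 read together. Withdrawal for non-compliance is allowed, and it ends endpoint collection in subjects who still have the device. The censoring may be informative and would then lower both 24-month primary rates. Selective loss is a risk, not a documented result.

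The size is unknown. Under evenly spread exits and a 4.5% rate in those retained, it is about 0.2 to 0.5 points at twice the risk (10% to 25% leaving) and 1.0 point at three times the risk with 25% leaving. The shares, relative risks and exit pattern are all assumptions. If only a few subjects are withdrawn this way, the effect is smaller still. The point merits action because follow-up can be kept at little cost, not because the conclusion is shown to be at risk. How the analysis treats withdrawn subjects cannot be judged from the redacted text.

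**What to change.** 1. In 7.7, delete "Subject's non-compliance" from the withdrawal reasons. Record it as a deviation and keep the subject in follow-up by visit or phone unless consent is withdrawn.
2. At every withdrawal or loss to follow-up, record on the Withdrawal eCRF whether an ischemic stroke, systemic embolism, listed device event or death has occurred since the last adverse event assessment, as consent permits.
3. Confirm in the redacted analysis text, or add, that a subject whose status is unknown is censored at the last completed adverse event assessment.

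Leave in place the investigator's discretion to withdraw a subject for other reasonable rationale. Narrowing it further would be a trade-off that this point does not justify.

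Cost: one edit to 7.7, one block on an existing form and at most one sentence on censoring. Sites will make some extra contacts, and the reported rates may be slightly less favourable. No sample size or visit changes.

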8.0 COMPLIANCE TO CIP

8.1 STATEMENTS OF COMPLIANCE

The study will be performed in accordance with the most current versions of the World Medical Association (WMA) Declaration of Helsinki and CFDA regulations and will be compliant to this International Standard and CFDA regulations, as appropriate.

Clinical Investigational Plan

The investigator will not start enrolling subjects or requesting informed consent from any subject prior to obtaining IRB/EC approval and authorization from the sponsor in writing for the study. The subject must sign the study informed consent form prior to implant procedure.

If additional requirements are imposed by the IRB/EC or CFDA, those requirements will be followed, if appropriate. If any action is taken by an IRB/EC, and regulatory requirements with respect to the study, that information will be forwarded to St. Jude Medical.

As the sponsor, St. Jude Medical has taken up local insurance policy in accordance with the requirements of the applicable local laws. Appropriate country representative will be utilized to understand the requirements for the type of insurance that will be provided for subjects, such information will be incorporated into the informed consent, as applicable

8.2 ADHERENCE TO THE CLINICAL INVESTIGATION PLAN

A deviation is defined as an event where the clinical investigator, site personnel, sponsor or sponsor representative did not conduct the clinical study according to the Clinical Investigational Plan, IRB/EC requirements or the Investigator Agreement. The investigator is not allowed to deviate from the CIP, except as specified under emergency circumstances.

In some cases, failure to comply with the CIP may be considered failure to protect the rights, safety and well-being of subjects, since the non-compliance exposes subjects to unreasonable risks. For example, failure to adhere to the inclusion/exclusion criteria: these criteria are specifically defined by the Sponsor to exclude subjects for whom the device is not beneficial and the use involves unreasonable risks. This may be considered failure to protect the rights, safety and well-being of the enrolled subject. Similarly, failure to perform safety assessments intended to detect adverse events may be considered failure to protect the rights, safety and well-being of the enrolled subject. Investigators should seek minimization of such risks by adhering to the CIP.

Simultaneously, in the event that adhering to the CIP might expose the subject to unreasonable risks, the investigator is also required to protect the rights, safety and well-being of the subject by intentionally deviating from the requirements of the CIP, so that subjects are not exposed to unreasonable risks.

It is the responsibility of the investigator to provide adequate medical care to a subject enrolled in a study.

Regulations require that the PI maintain accurate, complete, and current records, including documents showing the date of and reason for every deviation from the Clinical Investigational Plan. Relevant information for each deviation will be documented on a Deviation Case Report Form. The site will submit the CRF to St. Jude Medical.

Regulations require Investigators obtain approval from St. Jude Medical and the IRB/EC [as required] before initiating changes in or deviations from the protocol, except when necessary to protect the life or physical well-being of a subject in an emergency. Under emergency circumstances, deviations from the CIP to protect the rights, safety and well-being of human subjects may proceed without prior approval of the sponsor and the EC. Such deviations shall be documented and reported to the sponsor and the EC as soon as possible, but no later than 5 working days.

Clinical Investigational Plan

Prior approval must be requested when the PI anticipates, contemplates, or makes a conscious decision to depart from the CIP, except when unforeseen circumstances are beyond the investigator's control (e.g. a subject who fails to attend a scheduled follow-up visit, a subject is too ill to perform a CIP-required test, etc.). All deviations, including those beyond the investigator's control, must be reported on a CRF.

To obtain approval, the Principal Investigator may call or email and discuss the potential deviation with St. Jude Medical or designee prior to initiating any changes.

All deviations must be reported to appropriate regulatory authorities in specified timelines (if appropriate).

8.3 REPEATED AND SERIOUS NON-COMPLIANCE

In the event of repeated non-compliance or a one-time serious non-compliance, as determined by the Sponsor, a Clinical Research Associate or clinical representative will attempt to secure compliance by one or more of the following actions:

- Visiting the investigator
- Contacting the investigator by telephone
- Contacting the investigator in writing
- Retraining of the investigator

If an investigator is found to be repeatedly non-compliant with the signed agreement, the CIP or any other conditions of the clinical study, the Sponsor will either secure compliance or, at its sole discretion, terminate the investigator's participation in the clinical study.

